21.2 Sponsor

Prior to the commencement and for the duration of the clinical study, the sponsor shall

- 1) Select appropriately qualified Principal Investigators.
- 2) Ensure IRB/EC approval of protocol and informed consent, and that any future modification(s) required by the IRB/EC or regulatory authority are made and documented appropriately.
- 3) Obtain Investigator Agreement and curriculum vitae of all participating Investigators.
- 4) Ensure that a supply of investigational devices is available in a timely manner for the clinical investigation; ensure that investigational devices are not made available to the principal investigator until all requirements to start the clinical investigation are met. Ensure accountability of investigational devices throughout the clinical investigation
- 5) Ensure the members of the investigation site team and their designated authorizations(s) are identified in an log with details of responsibilities
- 6) Ensure documentation of training, for all the relevant parties involved in order to adequately conduct the study; includes training on use of the investigational devices, device accountability procedures, the Protocol and Investigators Brochure, CRFs and instructions for completion, the informed consent form and the consent process
- 7) Designate or appoint one or more monitors, or otherwise assume the responsibilities of the monitors
- 8) Investigate unanticipated, device related adverse effects
- 9) Document protocol deviations and violations
- 10) Maintain accurate and complete records relating to the investigation. These records include all correspondence including required reports, device accountability, monitoring reports and open action follow up, signed Investigator agreements including financial disclosure information, and records concerning complaints and adverse device effects whether anticipated or not
- 11) Provide the following reports in a timely manner to FDA, the IRB/EC, and/or the investigators.
 - (a) Unanticipated Adverse Device Effects
 - (b) Withdrawal of IRB or FDA Approval
 - (c) Current List of Investigators
 - (d) Recalls and Device Disposition
 - (e) Progress and Final Reports

21.3 Monitor

- A. Conduct the study initiation visit or meeting
- B. Conduct routine on-site monitoring visits to verify:
 - 1) Compliance to the protocol, any amendment(s), applicable regulations, and IRB / EC requirements
 - 2) Only authorized individuals are participating in the clinical study
 - 3) Investigational site resources remain adequate
 - 4) Signed and dated informed consent has been obtained for all subjects prior to initiation of study-specific screening assessments
 - 5) Source documents and other clinical study records are accurate, complete, up to date, and stored and maintained properly
 - 6) CRFs and queries are complete, recorded in a timely manner, and consistent with source documents
 - 7) Appropriate corrections, additions or deletions are made to the CRFs, dated, explained if necessary and initialed by the principal investigator or authorized designee; the monitor shall not make corrections, additions or deletions to the CRFs
 - 8) All adverse events and device deficiencies are reported to the sponsor, and all serious adverse events and device deficiencies that could have led to a serious adverse device effect are reported to the sponsor without unjustified delay,
 - 9) All SAEs and deviations are reported to the IRB/EC, if required
 - 10) Storage and investigational device accountability are correct and the traceability process is being followed
 - 11) Required reports, notifications, submissions and correspondence are maintained in the investigator's files and are accurate, complete, timely, legible, dated, and identify the clinical investigation
 - 12) Subject withdrawal has been documented and discussed with the principal investigator or authorized designee
 - 13) The principal investigator and investigational site team are informed and knowledgeable of all relevant document updates concerning the investigation, and
 - 14) Any corrective and preventive actions, as needed, have been implemented and are effective
- C. Prepare monitoring reports for submission to the sponsor. Provide a copy of the monitoring report or a summary of key findings to the principal investigator in writing. The report will include the date, investigational site information, name of the monitor and principal investigator, any other individuals contacted, a summary of what the monitor reviewed, observation(s) with regard to completion of previous action items,

significant findings, facts, deviations, conclusions, and recommended actions to be taken to secure compliance.

21.4 Central Reader (MRI Core Lab)

- A. Credential sites to assess ability to participate in the mandatory sequences
- B. Develop site-specific standardized protocols for MRI examinations at the clinical Sites to be used for both baseline and post-baseline studies
- C. Train and ensure competence of Clinical Site technologists
- D. Develop a protocol for HIPAA-compliant transfer of image data from Clinical Sites to Core Lab
- E. Assess, QC, and track all studies submitted
- F. Utilize standardized CAD (Computer-Assisted Diagnosis) technique for quantitative image analysis of baseline and post-baseline examinations
- G. Transfer all image and verified final reads with calculated volume measurements, changes from baseline and all follow-up reads
- H. Prepare final report for study MRI data

22 LIST OF APPENDICES

- Appendix A:** EuroQOL EQ-5D Questionnaire
- Appendix B:** Uterine Fibroid Symptom and Quality of Life (UFS-QOL) Questionnaire
- Appendix C:** Treatment Recovery Questionnaire
- Appendix D:** Assessment of Hemostasis
- Appendix E:** ACOG Practice Bulletin 84
- Appendix F:** Menstrual Diary [Pictorial Blood Loss Assessment Chart (PBAC)], and Completion Instructions
- Appendix G:** PBAC Scoring Instructions
- Appendix H:** Hormonal Washout Instructions
- Appendix I:** Overall Treatment Effect and Subject Satisfaction
- Appendix J:** Numeric Rating Scale (NRS-11)
- Appendix K:** Work Productivity and Activity Impairment Questionnaire: Specific Health Problem (WPAI:SHP)

2. LIST OF ABBREVIATIONS

AE(s)	adverse event(s)
ADE	adverse device effect
eCRF(s)	electronic case report form(s)
DMP	Data Management Plan
e.g.	exempli gratia (for example)
FAS	Full Analysis Set
FDA	Food and Drug Administration
FIGO	International Federation of Gynecology and Obstetrics
HMB	Heavy Menstrual Bleeding
ICH	International Conference on Harmonization
LOCF	last observation carried forward
N	number (sample size)
OTE	Overall Treatment Effect
PBAC	Pictorial blood loss assessment chart
PP	per-protocol
SAE(s)	serious adverse event(s)
SAS®	Statistical Analysis System (SAS® Institute Inc., Cary, NC)
SD	standard deviation
UFS-QOL	Uterine fibroid symptom and quality of life

3. INTRODUCTION

The Gynesonics VizAblate[®] System is an intrauterine ultrasound-guided radiofrequency (RF) ablation system for the treatment of symptomatic uterine fibroids using a minimally invasive transcervical approach. VizAblate is suitable in an inpatient or outpatient setting, and is intended to provide focal treatment of symptomatic fibroids responsible for HMB. This Statistical Analysis Plan (SAP) describes the analytical methods to be used to assess the safety and effectiveness of the VizAblate System in the treatment of symptomatic uterine fibroids.

4. STUDY OBJECTIVES

The objective of this study is to establish the safety and effectiveness of the VizAblate System in the treatment of symptomatic uterine fibroids.

5. INVESTIGATIONAL PLAN

5.1 Overall Study Design

The study is designed as a prospective, longitudinal, multicenter, single-arm cohort study with the subject serving as her own control.

5.1.1 Schedule of Screening Assessments

Table 1: Schedule of Screening Assessments

Assessment	Timing of Assessment Prior to Enrollment				Immediately prior to Treatment
	Any time	Within 3 years	Within 12 Months	Within 3 Months	
Demographics	X				
Medical / Surgical History					
Pelvic / Menstrual History (at least last 3 months, but 6 months is preferable)				X	
Pelvic / Menstrual Pain - Numeric Rating Scale (NRS-11)				X	
Menstrual Diary (Pictorial blood loss assessment chart or "PBAC")				X	
Vital signs (temperature, pulse, blood pressure, height, weight)				X	
Pelvic Exam				X	
Cervical cancer screening (per subject history with adherence to national guidelines)		X			
Endometrial biopsy			X		
TVUS and SIS OR TVUS and hysteroscopy (to confirm location & size of fibroids, assess for the presence of adenomyosis)				X	
Hemoglobin level					
Cervical GC and chlamydia testing				X	
Urine or serum hCG				X	
Serum creatinine				X	X
Hemostasis assessment				X	
ce-MRI (screen MRI). MRI's will be forwarded to a central reader.					X
UFS-QOL Questionnaire					X
EQ-5D Questionnaire					X
Birth control assessment					X
Concomitant medications			Ongoing		
Adverse events			Ongoing		
Final eligibility assessment			Ongoing		X

5.1.2 Schedule of Study Visits and Assessments

Table 2: Schedule of Study Visits and Assessments

Assessment	Baseline	Day 0 Treatment	FU Visit 1 10 day	FU Visit 2 30 day	FU Visit 3 3 mo	FU Visit 4 6 mo	FU Visit 5 12 mo	FU Visit 6 2 year	FU Visit 7 3 year
PBAC	[Screening assessment]					X	X		
EQ-5D	[Screening assessment]				X	X	X	X	X
UFS-QOL	[Screening assessment]				X	X	X	X	X
Vital signs as per screening		X							
Urine/serum hCG, (<24 hours pre-procedure)		X							
Venous thromboembolism risk classification		X							
Birth control adherence		X	X	X	X	X	X		
VizAblate Treatment & Procedure Assessments Procedure & discharge times, pain VAS & tolerance, anesthesia and concomitant medications		X							
Adverse events		X	X	X	X	X	X	X	X
Concomitant medications		X	X	X	X	X	X		
ce-MRI	[Screening assessment]						X		
Return to normal daily activity**				X					
Post-procedure follow up Update to medical history and symptoms			X	X	X	X	X		
Pregnancy /pregnancy outcome				X	X	X	X	X	X
OTE and Subject satisfaction						X	X	X	X
Surgical Reintervention*						X	X	X	X

* If subject undergoes hysterectomy, operative and pathology reports shall be forwarded to study sponsor
 **Subjects who are not back to normal activity will be followed weekly by phone until normal activity has resumed or is not expected to change

5.2 Selection of Study Population

5.2.1 Inclusion Criteria

- 1) Are premenopausal
- 2) Are ≥ 25 and ≤ 50 years of age at time of enrollment
- 3) Have experienced heavy menstrual bleeding associated with fibroids (AUB-L) for at least the previous three months as reported by the subject
- 4) Have ≥ 1 and ≤ 6 fibroids of FIGO types 1, 2, 3, 4, and/or type 2-5, with diameter ≥ 1.0 cm and ≤ 5.0 cm as determined by credentialed transvaginal sonography or magnetic resonance imaging (MRI). Fibroids of type 5, 6, and 7 do not count toward the clinically relevant total, irrespective of size.
- 5) Have at least one fibroid that indents the endometrial cavity.
- 6) Pictorial blood loss assessment chart (PBAC) score ≥ 150 and ≤ 500 during a single baseline cycle
- 7) Consistent menstrual cycles of between 22 to 35 days in duration that meet the following requirements for at least 4 of the last 6 menstrual cycles prior to enrollment as reported by the subject:
 - (1) Variations in cycle length of no more than +/- 4 days, and
 - (2) Bleeding duration of 3-10 days, in which the bleeding requires use of more than a pantiliner
- 8) Subject is not at material risk for pregnancy (not sexually active; has been sterilized; does not have a male partner or is in a monogamous relationship with a sterilized male partner; reliably uses barrier contraception with contraceptive foam, or oral or vaginal hormonal contraception. Subject is willing to maintain use or non-use of non-injectable hormonal contraception uniformly from 6 months pre-study through the 12-month follow-up period. Only monthly cyclic combined contraceptive steroids will be acceptable as oral contraception). If a subject is on oral/vaginal hormonal contraception solely for bleeding control, or if a subject does not wish to commit to 12 months of consistent hormonal contraceptive use, subject must discontinue use as per the washout period specified in Protocol Appendix H.
- 9) Speaks and reads a language for which validated questionnaires are available
- 10) Willing and able to read, understand, and sign the informed consent form, to participate in the study and to adhere to all study follow-up requirements

5.2.2 Exclusion Criteria

- 1) Pregnancy, as determined by urine or serum hCG obtained within 24 hours prior to treatment with VizAblate
- 2) Urgent need for surgery to treat fibroid symptoms
- 3) Desire for current or future childbearing
- 4) Presence of a tubal implant for sterilization
- 5) Postmenopausal by history
- 6) Presence of type 0 fibroids, unless < 1 cm in diameter and are unlikely to contribute to bleeding in the judgment of the investigator.
- 7) Presence of a single polyp ≥ 1.5 cm, or multiple polyps of any size, within the uterine cavity, or excision of polyps within three months of completing any screening procedures
- 8) Any fibroid of FIGO type 1, type 2, type 3, type 4, or type 2-5 with diameter > 5.0 cm as determined by transvaginal sonography or magnetic resonance imaging (MRI)
- 9) Bulk symptoms (pelvic pressure, frequent urination) that significantly interfere with normal daily activities in the presence of one or more fibroids of FIGO type 5, type 6, or type 7
- 10) Exclusive presence of fibroids that, despite meeting other eligibility criteria, are insufficient to explain the severity of symptoms in the judgment of the Investigator
- 11) Presence of clinically relevant fibroids that can not be treated for technical reasons (e.g. cervical fibroid)
- 12) Presence of an extrauterine pelvic mass
- 13) IUD/IUS in situ within the washout period specified in Protocol Appendix H prior to undergoing any screening procedures
- 14) Known prior fundal hysterotomy (e.g. classical c-section)
- 15) Previous endometrial ablation, uterine artery embolization, laparoscopic uterine artery occlusion, open/laparoscopic myomectomy or any other procedure for fibroids or heavy menstrual bleeding other than hysteroscopic myomectomy
- 16) Hysteroscopic myomectomy within 12 months prior to undergoing any screening procedures, or hysteroscopic myomectomy > 12 months with less than 6 months of symptom relief

- 17) Any abnormality of the endometrial cavity that, in the judgment of the Investigator, obstructs access of the VizAblate Handpiece to the endometrial cavity or fibroids (eg, significant intrauterine synechiae)
- 18) Contraindication to MRI, including MR-incompatible implants, allergy to contrast media or claustrophobia, and weight that is above the limitation of the site-specific MRI scanner credentialed for the study
- 19) Total uterine volume > 400 cc as determined by transvaginal sonography
- 20) Clinically significant adenomyosis based on sonography; presence confirmed by MRI (defined as more than 10% of the junctional zone measuring more than 10 mm in thickness as measured by MRI)
- 21) Confirmed or suspected diagnosis of clinically relevant endometriosis
- 22) One or more clinically relevant fibroids that are significantly calcified. If suspicion of calcification, refer to MRI (significant calcification is defined as being associated with < 75% fibroid enhancement by volume via contrast-enhanced MRI)
- 23) Previous pelvic irradiation
- 24) Hemoglobin level that does not meet the institutional presurgical requirement at time of treatment
- 25) Renal insufficiency [serum creatinine ≥ 1.5 m g/dL (132.6 μ mol/L)]
- 26) Evidence of disorders of hemostasis (AUB-C) as assessed through structured interview and confirmed by hematologic evaluation consistent with a coagulopathy (see Protocol Appendix D)
- 27) Abnormal cervical cytology that is unevaluated or untreated in adherence with national guidelines
- 28) Endometrial hyperplasia (AUB-M), including simple hyperplasia without atypia, as determined by an endometrial biopsy within 12 months prior to enrollment
- 29) Confirmed abdominal / pelvic malignancy within the previous five years
- 30) Active pelvic infection (e.g., active salpingitis or other pelvic inflammatory disease) or current positive testing for pelvic gonorrhea or chlamydia; entry into the study would require a test of cure after treatment
- 31) Use of a GnRH agonist, depot medroxyprogesterone acetate or other hormonally-relevant medication within the washout period as specified in Protocol Appendix H prior to undergoing any screening procedures
- 32) Use of an antifibrinolytic agent while undergoing any screening procedures.

- 33) Current use of anticoagulant therapy (warfarin derivatives or heparin)
- 34) Chronic pelvic pain (disruptive for at least six months) or baseline pelvic or menstrual pain > 6 as captured using the Numeric Rating Scale (NRS-11) as shown in Protocol Appendix J.
- 35) Uncontrolled hypertension lasting 2 years or more (systolic blood pressure \geq 140 mm Hg and/or diastolic blood pressure \geq 90 mm Hg that is not controlled with an antihypertensive drug regimen)
- 36) A hypoplastic or otherwise short uterus (distance from the top of the endometrial cavity to the external cervical os < 4.5 cm, as determined by transvaginal sonography or prior uterine sounding)
- 37) Major medical or psychiatric illness or other factors that, in the judgment of the Investigator may affect general health or subject's ability to adhere to the follow-up schedule or provide valid subject self-assessment data
- 38) Any other reason for which, in the opinion of the Investigator, the individual study subject is not appropriate or suitable for participation in the clinical trial

5.3 Treatments

The VizAblate System is intended for the transcervical treatment of symptomatic uterine fibroids, including those associated with HMB, under intrauterine ultrasound guidance.

5.4 Data Management

Data collected for the study will be entered into a web-based system through electronic Case Report Forms (eCRFs) by each investigational site. The Electronic Data Capture (EDC) system maintains a complete electronic audit trail enabling full compliance with 21 CFR Part 11 and GCP guidelines. The design and specification of eCRFs as well as edit checks will be in accordance with the study requirements. Prior to database lock, the following steps must be completed: data entry or transferring as required per protocol, source verification, query resolution, data review by clinical data managers and final sign-off by site principal investigators.

For statistical analysis, data stored in the central database will be exported to SAS® files (SAS Institute Inc, Cary, NC, USA). The data extract from the final locked database will be used to generate the final clinical study report.

5.5 Efficacy and Safety Variables

5.5.1 Co-Primary Efficacy Variables

5.5.1.1 Pictorial Blood Loss Assessment Chart (PBAC)

Subjects will be asked to assess menstrual bleeding using a PBAC menstrual diary. The PBAC is a visual representation of blood loss from which a numerical score is derived. The PBAC is detailed in Appendix D. PBAC scoring instructions are included in Appendix E.

5.5.1.2 Surgical Reintervention

Subjects will be asked to indicate whether there has been any surgical reintervention for the treatment of HMB since their last visit. The rate of surgical reintervention for HMB due to treatment failure will be evaluated throughout all assessment timepoints and at 12 months as a co-primary endpoint. Surgical reintervention for the treatment of HMB includes the following procedures:

- a) Hysterectomy (abdominal, vaginal, laparoscopic)
- b) Myomectomy (abdominal, vaginal, laparoscopic, hysteroscopic)
- c) Uterine artery embolization
- d) Magnetic resonance-guided focused ultrasound (MRgFUS) or similar focused ultrasound treatment
- e) Endometrial ablation (nonresectoscopic, hysteroscopic)

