9.1 CO-PRIMARY ENDPOINTS & SUCCESS CRITERIA

Table 1 provides a list of the test method, subject success criteria, and study success criteria for the co-primary endpoints. The co-primary endpoints are reached at 12 months.

Table 1 Co-Primary Endpoints & Success Criteria

Co-Primary Endpoint	Test Method	Subject Success Criteria ^{Note 1}	Study Success Criteria ^{Note 2}
Reduction in Menstrual Blood Loss (MBL) at 12 months	Pictorial blood loss assessment chart (PBAC), Appendix F. This is a validated measure of MBL ⁹ . Scoring instructions are included in Appendix G.	≥ 50% reduction in PBAC score, and a final PBAC score < 250	LCL of the percentage of subject success ≥ 45%
Rate of surgical re-intervention for HMB due to treatment failure at 12 months	Surgical re-intervention for HMB due to treatment failure	No surgical re-intervention for HMB due to treatment failure at 12 months	LCL of the percentage of subject success ≥ 75%

Table Notes

- 1) Subject success is calculated separately for the two co-primary endpoints, such that it is possible for a subject to be considered a success for one co-primary endpoint and not for the other.
- 2) Study success is achieved if both of the study success criteria are met.

⁹ Janssen C, Scholten P, Heintz P. A simple visual assessment technique to discriminate between menorrhagia and normal menstrual blood loss. *Obstet & Gynec.* 1995;85:977-982.

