Birth control adherence		X	X	X	X	X	X		
Sonata Treatment & Procedure Assessments Procedure & discharge times, pain VAS & tolerance, anesthesia and concomitant medications		X							
Adverse events		X	X	X	X	X	X	X	X
Concomitant medications		X	X	X	X	X	X		
ce-MRI	[Screening assessment]						X		
Return to normal daily activity**				X					
Post-procedure follow up Update to medical history and symptoms			X	X	X	X	X		
Pregnancy /pregnancy outcome				X	X	X	X	X	X
OTE and Subject satisfaction						X	X	X	X
Surgical Reintervention*						X	X	X	X

* if subject undergoes hysterectomy, operative and pathology reports shall be forwarded to study sponsor

**Subjects who are not back to normal activity will be followed weekly by phone until normal activity has resumed or is not expected to change

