- A supply of sanitary products in sufficient quantity to cover use for one menstrual cycle for the completion of the PBAC.

- 4) Follow-up Visits #4-5: 6 Months (\pm 4 weeks) and 12 Months (\pm 2 Months)
- (a) MRI (12 months only)
 - (b) UFS-QOL, EQ-5D, and WPAI:SHP Questionnaires
Subjects will be asked to return their completed EQ-5D questionnaire and will be asked to complete the UFS-QOL and WPAI:SHP questionnaires.
 - (c) Menstrual Diary
Subjects will be asked to return their completed menstrual diary (PBAC) for the menstrual cycle preceding the visit.
 - (d) Adverse Events
Subjects will be asked if they have experienced any untoward medical occurrences since the Sonata treatment. If so, these events will be recorded on the Adverse Event case report form, in accordance with the procedures outlined later in this protocol.
 - (e) Surgical Reintervention
Subjects will be asked if they have undergone any surgical procedure to treat their heavy menstrual bleeding. If so, the procedure performed and the date of the reintervention will be recorded.
 - (f) Pregnancy/Pregnancy Outcomes
Subjects will be asked if they have become pregnant since the last follow-up visit. If so, the subject will be released from all protocol specified follow-up assessments and visits, however the subject will be followed and pregnancy outcomes (including any complications) will be recorded as described in Section 10.6 of this protocol.
 - (g) Post-treatment follow-up
Subjects will be asked whether there is any change to their medical status. Subjects will be asked specifically if they have experienced any signs of fibroid shedding: cramping, bleeding, passage of any tissue per vaginam.
 - (h) Amenorrhea
If the subject becomes amenorrheic, a pregnancy test (urine or serum hCG) will be performed and, if negative, a serum FSH level determination will also be obtained.
 - (i) Concomitant Medications
Subjects will also be asked about concomitant medications, noting concomitant medications taken for the treatment of excessive uterine bleeding.

(j) Subject Satisfaction

Subjects will be asked to rate their satisfaction with the treatment, with responses based on a 6-point Likert scale ranging from “very satisfied” to “very dissatisfied”. They will also be asked if they would recommend the treatment to a friend with the same health problems using a 4-point scale from “definitely yes” to “definitely not”.

(k) Overall Treatment Effect (OTE)

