14.1 Definitions¹⁴

A. Adverse Event (AE)

Any untoward medical occurrence, unintended disease or injury or any untoward clinical signs (including an abnormal laboratory finding) in subjects, users or other persons whether or not related to the investigational medical device.

NOTE 1: This includes events related to the procedures involved.

NOTE 2: For users or other persons this is restricted to events related to the investigational medical device.

NOTE 3: An elective surgical reintervention for HMB or change in a measured endpoint is not considered an adverse event.

NOTE 4: An overnight stay for observation does not constitute hospitalization for the purposes of this protocol as long as there are no reported adverse events associated with the stay.

B. Adverse Device Effect (ADE)

Adverse Event related to the use of a medical device. This includes:

- 1) Any adverse event resulting from insufficiencies or inadequacies in the instructions for use, the deployment, the installation, the operation, or any malfunction of the medical device.
- 2) Any event that is a result of a use error or intentional misuse.

C. Anticipated

An effect which by its nature, incidence, severity or outcome has been previously identified in the risk analysis.

D. Device Deficiency

Inadequacy of a medical device with respect to its identity, quality, durability, reliability, safety or performance. This includes malfunctions, use errors, and inadequate labeling.

E. Malfunction

Failure of an investigational medical device to perform in accordance with its intended purpose when used in accordance with the instructions for use or Clinical Investigation Plan.

¹⁴ Reference ANSI/AAMI/ISO 14155:2011

- F. Serious Adverse Event (SAE)
Adverse Event that
- 1) Led to death
 - 2) Led to a serious deterioration in the health of the subject that either:
 - (a) resulted in a life-threatening illness or injury, or
 - (b) resulted in a permanent impairment of a body structure or a body function, or
 - (c) required in-patient hospitalization, or prolongation of existing hospitalization, of more than 24 hours, or
 - (d) resulted in medical or surgical intervention to prevent life threatening illness or injury or permanent impairment to a body structure or a body function.
 - 3) Led to fetal distress, fetal death or congenital abnormality or birth defect

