5.6.4.1 Primary Efficacy Analysis

Table 3 describes the two co-primary endpoints. Each subject will be determined to be a Success or Failure per the subject success criteria. For the endpoint of Reduction in Menstrual Blood Loss, the count and percentage of subjects with Success and Failure will be summarized, along with the 95% exact confidence interval for the percent successes. The rate of surgical reintervention during 12 months, along with 95% confidence interval, will be determined using Life-Table methods. Each endpoint has a pre-specified study success criterion, as described in Table 3. Study success is achieved if both of study success criteria are met.

Table 3: Co-Primary Endpoints and Success Criteria

Co-Primary Endpoint	Test Method	Subject Success Criteria ^a	Study Success Criteria
Reduction in MBL at 12 months	Modified pictorial blood loss assessment chart (PBAC)	≥ 50% reduction in PBAC score, and a final PBAC score < 250	LCL of the percentage of subject success ≥ 45%
Rate of surgical reintervention for HMB due to treatment failure at 12 months	Surgical reintervention for HMB due to treatment failure	No surgical reintervention for HMB due to treatment failure at 12 months	LCL of the percentage of subject success ≥ 75%

^a Subject success is calculated separately for the two co-primary endpoints, such that it is possible for a subject to be considered a success for one co-primary endpoint and not for the other.

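### The plan conflicts on whether every listed operation for HMB counts as a reintervention event, because the success criterion adds an undefined treatment-failure condition that can only remove events

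*SAP*

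**What the plan says.** **Success criterion.** Protocol Table 1 (section 9.1) defines subject success as "No surgical re-intervention for HMB due to treatment failure at 12 months". SAP Table 3 (5.6.4.1) agrees: "No surgical reintervention for HMB due to treatment failure at 12 months". SAP 5.5.1.2 carries the same condition: "The rate of surgical reintervention for HMB due to treatment failure will be evaluated throughout all assessment timepoints". A failure therefore needs two things: surgery for HMB, and a judgement that it resulted from treatment failure.

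**Procedure list.** SAP 5.5.1.2 introduces five procedure classes with "Surgical reintervention for the treatment of HMB includes the following procedures". The list settles the first element only. Neither document defines treatment failure.

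**Data described.** The SAP's question is about surgery for HMB in general: "Subjects will be asked to indicate whether there has been any surgical reintervention for the treatment of HMB since their last visit". In Protocol 12.3, when a woman reports such surgery, "the procedure performed and the date of the reintervention will be recorded". Cause is not among the items described. The footnote to Protocol Table 4 adds, for one procedure only: "if subject undergoes hysterectomy, operative and pathology reports shall be forwarded to study sponsor". It gives no reader, rule or use for those reports.

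**Review.** The Medical Advisory Board reviews adverse events, device deficiencies and deviations (Protocol 14.3 and 17.3; SAP 5.6.8.3). Protocol 14.1 states: "An elective surgical reintervention for HMB or change in a measured endpoint is not considered an adverse event". Elective HMB surgery therefore does not reach the Board as an adverse event.

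**Analysis text.** The life-table sentences in SAP 5.6.4.1 and 5.6.8.2 speak of surgical reintervention during 12 months without the causal condition. The heading over the 5.6.8.2 paragraph keeps it.

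**The concern.** Two statisticians working from these documents could score the same operation differently. Take a hysterectomy for HMB at month 8. Under the success tables it is a failure only if someone attributes it to treatment failure. Under the life-table sentences it is an event because it is a reintervention.

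The ambiguity runs in one direction. There is no control arm in which the same judgement would be made, nobody is blinded, and the condition can turn an event into a non-event but never the reverse. If an operation is discounted, the SAP does not say whether the woman stays event-free or is censored at surgery. Neither is a failure.

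The other co-primary does not catch the case. SAP 5.6.8.2 removes women reoperated for fibroid symptoms before month 12 from the menstrual blood loss analysis. A woman whose HMB operation was discounted could therefore fail neither co-primary.

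**Working it through.** **Inputs from the documents.** Threshold for the lower confidence limit (LCL) 75% and assumed success rate 90% (Protocol 19.1 B, SAP Table 4); 95% interval; N = 75 for better than 90% power; 147 women to be treated (Protocol 19.1 C).

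**Inputs that are assumptions.** The share d of HMB operations judged not due to treatment failure; the documents give no value, so 10%, 20% and 30% are shown. Complete follow-up. An exact binomial limit in place of the life-table limit.

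**Step 1: reproduce the plan's figure.** With x successes in n, the exact lower limit is the 2.5% quantile of Beta(x, n − x + 1).
- At n = 75, 64 successes give 75.27% and 63 give 73.72%, so at most 11 events are allowed.
- Power = P(X ≤ 11 | n = 75, event rate 0.10) = 0.931.
- Probability of passing at the boundary = P(X ≤ 11 | n = 75, event rate 0.25) = 0.022.
- 75 is also the smallest n from which power stays at or above 90% for every larger n checked (up to 179).

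The stated N reproduces and is not in dispute.

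**Step 2: decision rule at 147.** 121 of 147 gives an LCL of 75.17% (met); 120 of 147 gives 74.41% (missed). At most 26 events are allowed.

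**Step 3: effect of discounting.** If the true rate of any HMB operation is r, the counted rate is r × (1 − d), and the chance of passing is P(X ≤ 26 | n = 147, r(1 − d)). At r = 25%:

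| Discounted share d | Counted rate | Chance of passing, n = 147 | n = 125, at most 21 events |
|---|---|---|---|
| 0% | 25.0% | 2.2% | 1.9% |
| 10% | 22.5% | 9.5% | 7.5% |
| 20% | 20.0% | 28.0% | 22.0% |
| 30% | 17.5% | 57.6% | 47.5% |

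The last column shows that the pattern does not depend on all 147 women being followed.

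**Step 4: a concrete case.** 31 HMB operations leave 116 of 147 successes, LCL 71.4%, and the goal is missed. If five of the 31 are discounted, 26 events remain, the LCL is 75.17%, and the goal is met.

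**Step 5: at the planned rate.** At r = 10%, P(X ≤ 26 | 147, 0.10) = 0.9986 with nothing discounted. Discounting cannot usefully raise that. Only the reported rate moves: 10% × 0.9, 0.8 or 0.7 = 9%, 8% or 7%.

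**The case against.** The strongest reply is that the condition may be merely descriptive. If sites record only procedure and date, the described data hold nothing with which to discount an operation, and the life-table sentences contain no filter. On that reading every listed HMB operation already counts. This is a fair reading, and it is why the point is a conflict to be settled and not an established route to losing events. It does not dispose of the matter, because both success tables and the SAP 5.6.8.2 heading keep the condition, and the success tables are what decide the trial.

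Four stronger claims that a reader might infer are not supported:
- **That cause is not collected.** The case report form is not among the documents, and Protocol 15.1 requires hospital charts with operative reports. One can say only that neither document describes collecting it.
- **That the filter is post hoc.** The condition is part of the pre-specified definition. What is missing is a rule for applying it.
- **That particular causes would be discounted.** No text says that surgery for an untreated or new fibroid, or from patient preference, would be set aside. Protocol 12.2 E intends all clinically relevant fibroids to be ablated in one session, so surgery for an untreated one might well be judged treatment failure. Some genuinely separate causes already have rules, in Protocol 10.6 E and SAP 5.6.1.
- **That 9.5%, 28% and 58% are error rates of the plan as written.** They are wrong passes only against an endpoint that counts all HMB surgery. If some discounted operations truly were not treatment failures, the rate the plan defines is below 25%.

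**Conclusion.** The concern holds as a conflict over which operations count. The binding criterion contains a causal condition with no definition, no described data item and no named decision-maker, while the analysis sentences leave the condition out. Where it is applied, it can only lower the event count.

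The size is illustrative. At a true HMB reoperation rate of 25%, discounting 10% to 30% of operations takes the chance of meeting the goal from 2.2% to between 9.5% and 58%. This rests on an assumed discounted share, 147 women without censoring (the protocol expects 15% dropout), and an exact limit standing in for the life table. At the planned 10% rate the pass decision is unaffected, and the consequence is at most an understated reintervention rate. The point should be settled before analysis, but it does not undermine the sample size.

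**What to change.** In Protocol Table 1, SAP 5.5.1.2 and SAP Table 3, state that any procedure on the SAP 5.5.1.2 list performed to treat HMB within 12 months of treatment is a co-primary event in the full analysis set, whatever the attributed cause. Leave the full analysis set exclusions in SAP 5.6.1 unchanged. Report the treatment-failure subset as supportive only, with the investigator's reason recorded on the reintervention form.

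**Cost.** Protocol and SAP wording, plus one form field if the reason is not already captured; no extra visits. N = 75 stands if the assumed 90% means freedom from any such operation. An occasional unrelated HMB operation will count as an event, so the reported rate may be slightly less favourable. Someone must still decide that the surgery was for HMB. Because the change concerns an endpoint, Protocol 16.2 B requires IRB/EC approval before it is implemented.

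**Minimum, if the co-primary wording is kept.** Pre-specify a sensitivity analysis that counts all listed HMB procedures as failures.
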